## Section I.0- Project Overview

VA MapTrek is a mobile-phone-based web application that allows participants to take a virtual walk in interesting locations around the world while tracking their progress against the progress of other veterans on an interactive map. Steps are counted using a commercially-available triaxial accelerometer (e.g., Fitbit), and users see their progress overlaid on Google Maps. Our objective is to report activity levels to veterans, thereby encouraging them to walk more. Once participants know how to text and use Google maps, no additional training is needed. VA MapTrek does not require a special app, so there are no logins or passwords to remember. Simply registering one's Fitbit and mobile phone at an initial enrollment meeting suffices.

### Section I.1 Background Information

Nearly one-third of all veterans are obese, and an additional 44% are overweight. Obesity is a known risk factor for hypertension, coronary artery disease, type two diabetes, and multiple forms of cancer, all common medical problems affecting US veterans. Among veterans who are obese, 75% report the desire to lose weight, but 59% of these individuals are either inactive or irregularly active. Even moderate amounts of physical activity, e.g., 30 minutes of walking per day, can facilitate weight loss in overweight and obese individuals. Increased time walking is also associated with increased quality of life in all domains, including decreased depressive symptoms in older men. The prevalence of obesity and associated medical problems in veterans using VA services highlights the need for new interventions to help increase physical activity, specifically walking, among US veterans.

The VA has taken steps to improve health through lifestyle changes, specifically through the MOVE! Weight Management Program and the Whole Health Clinic. While proving to be successful, these programs require attendance at a VA location and only last for a finite period of time. Upon program completion, there is an unmet need to provide continued engagement. Ideally, the solution would be to offer a program suitable for long-distance deployment, especially to veterans living in rural areas. This program should also scale to expand in a cost-effective manner to serve veterans in all areas without requiring significant additions of personnel or increasing workloads in existing VA staff. The goal of our study is to test the feasibility of using our new VA-specific version of MapTrek to incentivize veterans to engage in or maintain an active lifestyle.

VA MapTrek, an m-health intervention developed by collaborators at the University of Iowa, is a mobile-phone-based web app that allows users to take a virtual walk in interesting locations around the world while tracking their progress against that of others like themselves on an interactive map. Steps are counted by a commercially-available Fitbit triaxial accelerometer, and users see their progress overlaid on Google Maps. The objective is to report activity levels in the virtual environment to veterans, thereby encouraging them to first, walk more every day, and second, maintain these new increased levels of physical activity. Communication occurs via SMS text messaging, a ubiquitous communication medium. Using familiar technologies makes VA MapTrek easy to use. It does not require additional apps, logins, or passwords to remember. Registering a Fitbit and mobile phone during one appointment at a VA clinic allows play for the entire study.

## Section 1.2 Research Questions

The purpose of the proposed project is to contribute to and improve upon the existing weight management and physical-activity-promoting programs available to veterans. Our specific objectives are to:

- 1) Assess the effectiveness of VA MapTrek as a whole to increase steps per day in veterans compared to the control group.
- 2) Assess the effectiveness of challenges within VA MapTrek to increase steps per day in veterans in the intervention group.
- 3) Identify additional areas of development within the MapTrek program to improve its future efficacy among veterans.

## Section 1.3 Project Outline

All consented participants will be provided with a Fitbit and instructed to wear it all day, every day for the next 9 weeks (The first few participants may require an additional week or two of wear as we will not begin the first MapTrek race until we have at least 5 participants enrolled in the study. They will be told this upon enrollment.). We expect the enrollment process to take anywhere from 15 to 45 minutes, depending on group assignment and participant familiarity with using Fitbits.

This, plus an exit survey (given via text message or phone, whichever the participant prefers), will be the extent of participation for the control group.

Members of the intervention group will be instructed on how to use MapTrek, our virtual walking race, and will also be given an instruction packet to refer to later. Data collected during the first week from the Fitbit will be used to compute baseline activity level. This baseline data will be used to place participants into an appropriate initial race group. Participants are placed into groups with other individuals who are active at a similar level, so that groups will be competitive.

Each virtual walking race will begin on Monday morning and end on Saturday night. Results of each race will be announced on Sundays. Depending on their performance each week, group assignment may change. Participants will compete in 8 week-long races over the course of the study.

Participants will receive 2-4 text messages per day including a daily status report and a link to view the race. They will also periodically receive challenge messages. If a participant completes a challenge, they will be awarded bonus steps to help move them along the route quicker.

To win a race, a participant must be furthest along on the route at 11:59 pm on Saturday. There is a leaderboard within MapTrek that helps participants determine their standing within each race. Participants are allowed to choose the screen name displayed on the leaderboard so that they may remain anonymous if desired.

At baseline, we will collect the following data about all participants: first and last name, last 4 of social security number (for consent documentation and to look up records in CPRS), age, sex, race,

ethnicity, marital status, height, weight, body mass index, blood pressure, zip code, current medications, and comorbidities.

At the end of the study (9 weeks), we will collect the following data about all participants: height, weight, body mass index, blood pressure, current medications, and comorbidities.

At the end of the study (9 weeks), we will also contact participants via text message or phone call (based on their preference at baseline) to complete an exit survey. We anticipate this survey taking approximately 10 minutes to complete. We will attempt to contact all participants up to 3 times to complete the exit survey. If they cannot be reached, they will be considered lost to follow up.

## Section 2.0- Participant Enrollment Procedures

### Section 2.1 Consort Flow Diagram Data

Prior to enrolling any participants, we need to begin tracking the number of people who are eligible for our study, how many we contact, how many enroll, etc. To do this, make sure that you are filling out a Screening Survey in REDCap for anyone that is considered for enrollment in the study.

### Section 2.2 Arrival at the Clinic

TBD

### Section 2.3 Screening

Prior to enrolling participants, eligibility must be assessed. This may be done by asking the person or by screening CPRS first and then finishing the remaining questions with the potential participant. Everyone should be screened for:

- 1) Comfort speaking and reading in English (must be yes)
- 2) Age (must be 18-100 years)
- 2) Smartphone with text messaging and internet capabilities (must be yes)
- 3) Current Fitbit account (doesn't matter)
- 4) Male or Female (doesn't matter)
- 5) Current height (in inches) (You must indicate the date the height was measured/reported. If they are self-reporting it, put today's date; if it is from CPRS, indicate the date it was logged in CPRS)
- 6) Current weight (in pounds) (You must indicate the date the weight was measured/reported. If they are self-reporting it, put today's date; if it is from CPRS, indicate the date it was logged in CPRS)
- 7) BMI (REDCap will calculate, must be  $\geq 25$ )
- 8) Text message or phone call exit survey preference (doesn't matter)
- 9) Record if the height/weight were self-reported or from CPRS
- 10) Determine if the potential participant is eligible
- 11) Indicate if they were randomized to the intervention group or control group
- 12) Include any relevant notes that we may need to know later

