### **Section 2.6 Randomization Procedures**

To determine which group the participant will be placed into, grab one folder from each pile (Intervention and Control) and let the participant choose one. If the folder contains the MapTrek instruction packet (Appendix D), they are in the intervention group. If the folder contains the fake paperwork, they are in the control group.

Be sure to note the group assignment in the Screening Survey and mark the survey as complete.

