### **Section 2.7 Control Group Instructions**

If the participant was assigned to the control group, the following tasks need to be completed before they leave the appointment:

- 1) Give the participant the Fitbit®. Instruct them on how to keep it charged and help them put it on for the first time.
- 2) Help the participant create a Fitbit® account by having them download the Fitbit® app from their app store and follow these steps:
  - 1) Make sure their phone's Bluetooth is turned on.
  - 2) Once the app is downloaded, open the app and click 'Join Fitbit'.
  - 3) Choose 'Charge 3' as the Fitbit Tracker.
  - 4) Click 'Set Up Your Fitbit Charge 3'
  - 5) Click 'Let's Go'
  - 6) Have them scroll up or down to their current height. Click 'Next'.
  - 7) Select their gender by clicking on the appropriate picture. Click 'Next'.
  - 8) Have them scroll left or right to their current weight. Click 'Next'.
  - 9) Have them scroll left and right to input their birth date. Click 'Next'.
  - 10) Have them enter their Full Name, Email Address, and Password. They will need to agree to the Terms of Service and Privacy Policy by clicking the check mark. Let them choose if they would like to receive news and promotions from the company.
  - 11) Click 'Next' to get past the Terms of Service and Privacy Policy screen.
  - 12) Let them Meet their Charge 3 by clicking 'Next' through the tutorial page.
  - 13) You may need to plug the Charge 3 in to complete set up.
  - 14) Make sure the Charge 3 is awake and close to the phone so that they can sync.
  - 15) Once it syncs, it will ask for the 4-digit number of the Fitbit screen.
  - 16) Click 'Next' and 'Done' to get through some tutorial information.
  - 17) They will then be logged into the Fitbit app. They may have a warning that email verification is required. They can do this at a later time.
  - 18) Show them that steps, distance, calories, and minutes of exercise are tracked on the dashboard.

3) Enroll the participant in the Control Group Boomerang Study by visiting <https://vinci.cs.uiowa.edu/meditext2> . Even though they will not be using MapTrek, they need to be entered into the Boomerang Study so that we can obtain the data from their Fitbit®.

- Log in using your username and password
- Select VA FY19-20 Control from drop down menu
- Click on the Green “Enroll Patient” button in the top right corner
- Enter the participant’s phone number, click Next

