**Editing existing Record ID 1**

Event Name: **Screening**

|   |   |
|---|---|
| Record ID   | 1   |
| 1. Are you comfortable speaking and reading in English  |  Yes
 No
<small>If no, ineligible</small>             |
| 2. What is your current age?  | 
<small>Participants younger than 18 or older than 100 are ineligible.</small> |
| 3. Do you own a smartphone with text messaging and internet capabilities?   |  Yes
 No
<small>If no, ineligible</small>             |
| 4. Do you already have a Fitbit account?  |  Yes
 No   |
| 5. Are you male or female?  |  Male
 Female  |
| 6. What is your current height (in)?  |   |
| For office use only: Date height was measured/reported  |   M-D-Y                                       |
| 7. What is your current weight (lb)?  |   |
| For office use only: Date weight was measured/reported  |   M-D-Y                                       |
| Calculated BMI  |  View equation
<small>if < 25, ineligible</small>           |
| 8. If you are enrolled in the study, would you prefer your exit survey via a text message or phone call?                              |  Text message
 Phone call                                |
| For office use only: Were height/weight/BMI self-reported or from CPRS?   |  Self-reported
 CPRS                                     |
| For office use only: Is the participant eligible?   |  Yes
 No   |
| For office use only: Randomized to intervention or control?   |  Control
 Intervention                                   |
| For office use only:  |   |
| Notes:  |   |
| Expand  |   |
| Form Status  |   |
| Complete?   |                                         |
| Lock this record for this form?  |   |

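### Whether the phone can run the Fitbit app and sync the study Charge 3 is first tested after the arm is known, so a person with no obtainable step data can be randomised

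*Protocol*

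**What the plan says.** Section 2.3 of the protocol lists the phone requirement as "Smartphone with text messaging and internet capabilities (must be yes". The Appendix A form puts it as an ownership question: "Do you own a smartphone with text messaging and internet capabilities". Holding a Fitbit account is recorded but is not a criterion: "Current Fitbit account (doesn't matter". Neither list mentions Bluetooth, compatibility with the Fitbit app, or a trial sync.

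Consent follows in Section 2.5. In Section 2.6 staff "grab one folder from each pile (Intervention and Control) and let the participant choose one", which reveals the arm; they then enter the assignment on the screening survey and close it.

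App download, Bluetooth, account creation and pairing appear only in Section 2.7 (control) and Section 2.8 (intervention), each conditional on the assignment. Both contain the same 18 sub-steps, including "Make sure the Charge 3 is awake and close to the phone so that they can sync". Both say that the listed tasks are to be finished at the appointment. The Fitbit account is then linked to Boomerang for control and to MapTrek for intervention, and step data reach the study through that link.

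The SAP models step counts from after the start of the intervention. It defines no analysis set and no handling of randomised participants without step data.

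**The concern.** Steps per day is the outcome in the first research question (Section 1.2), and the linked Fitbit is its only source. Baseline activity comes from the same device in the first week of wear (Section 1.3). A participant whose phone never syncs therefore has neither baseline nor outcome steps and contributes no rows to the SAP's mixed model.

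If this is found before allocation, the person is simply not randomised and the comparison is untouched. If it is found afterwards, the trial has either a post-randomisation exclusion or a randomised participant with no data, and nothing in the text available for review says which, or what staff should do. The screening survey feeds the CONSORT flow diagram (Section 2.1) but is closed before set-up begins. It has a free-text notes box and no field for set-up success, so such a loss has no designated place in the record.

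Staff and participant also both know the arm during set-up. If effort differed by arm, the people observed in the two arms could differ too.

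**Working it through.** **Step 1. Order of procedures.** The plan gives no figure to reproduce: neither document states a sample size, a power or a set-up failure rate. The claim is about sequence.

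1. Section 2.3 and Appendix A: phone with texting and internet. No app, Bluetooth or sync check.
2. Section 2.4: only people who meet all criteria go on to consent.
3. Section 2.5: consent signed.
4. Section 2.6: folder drawn, arm known, screening survey closed.
5. Sections 2.7 and 2.8: first app install, first pairing, first sync.

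The 18 sub-steps at item 5 are identical in the two arms, so nothing in their content requires them to follow item 4. What does depend on the arm is the Boomerang or MapTrek enrolment and, for intervention, the instruction packet.

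**Step 2. Equal loss in both arms.** Let f be the share who cannot complete set-up. The documents do not give f; 2% to 10% is an assumption. Treating information as proportional to the number of participants with data, the standard error is multiplied by 1/√(1−f). The number to randomise for 100 participants with data is 100/(1−f), rounded up.

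| f (assumed) | SE multiplier | Randomise for 100 with data |
|---|---|---|
| 2% | 1/√0.98 = 1.010 | 103 |
| 5% | 1/√0.95 = 1.026 | 106 |
| 10% | 1/√0.90 = 1.054 | 112 |

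**Step 3. Unequal loss.** Every input here is assumed. Let m be the mean daily steps of people whose set-up is easy, s the share with difficult set-up, D the number of steps by which they walk less, and q the share of an arm that is lost, all from the difficult group. With no true effect, the observed arm mean is m − D(s−q)/(1−q). Take s = 10%.

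- Control loses 10%, intervention 5%, D = 1,500. Control mean = m. Intervention mean = m − 1,500 × 0.05/0.95 = m − 78.9. Shift, intervention minus control: about −79 steps/day.
- Intervention loses 10%, control 5%, D = 1,000 to 2,000: shift of about +53 to +105 steps/day.
- Intervention loses 10%, control none, D = 1,000 to 2,000: shift of +100 to +200 steps/day.
- Equal loss: no shift.

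The sign depends on which arm loses more. A gap that is constant over time would move the SAP's group term and leave the group-by-days interaction unchanged. The SAP keeps baseline step data out of the model, so baseline would not adjust for the shift.

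**The case against.** The strongest reply is that the plan already contains a safeguard. Set-up is done in person with staff help, follows the same sub-steps in each arm, and is to be finished before the participant leaves. No failed pairing is reported. This stands: outright failure is probably uncommon, and the text supports saying only that such a person *can* be randomised.

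A reader might go further and infer that set-up effort favours one arm. Step 1 of the control list says "Instruct them on how to keep it charged and help them put it on for the first time", while step 1 of the intervention list only hands over the device. The documents do not support that inference. Both lists later have the participant put the device on, and both mention plugging it in during set-up. The remaining difference is an explicit charging instruction, which is not pairing. The remark in Section 1.3 that visit length varies, "depending on group assignment and participant familiarity with using Fitbits", concerns duration and says nothing about failure. The unequal-loss figures likewise need staff to depart from the completion rule in one arm, which nothing in the text suggests.

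It can also be said that feasibility is part of the stated goal (Section 1.1), so set-up failures should stay visible. They would: they can be counted just as well before randomisation.

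Finally, one successful sync does not secure nine weeks of data, and the platform link that differs by arm would still follow allocation. Both points are true and limit what the change achieves. They do not argue against removing a loss that can be prevented.

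**Conclusion.** The point holds as a matter of sequence. A prerequisite for having any step outcome is not part of eligibility and is first tested after the arm is known, so a person with no obtainable step data can be randomised and then lost, and the SAP has no rule for that case.

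The size is small as far as the documents allow it to be judged. With an assumed 2% to 10% failure, equal in both arms, the cost is a standard error about 1% to 5% larger. The bias figures, roughly 50 to 200 steps/day in either direction depending on which arm loses more, rest wholly on assumed inputs and show scale only. The documents do not show that anyone was lost this way, that loss differed by arm, or that the result is biased. This is a low-cost improvement to the procedures, together with a gap in reporting.

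**What to change.** 1. Keep the Section 2.3 phone question as a pre-consent screen. Optionally add whether the phone has Bluetooth and can install the Fitbit app. The sync test itself should not become a Section 2.3 criterion: Section 2.4 admits to consent only people who meet every criterion, so participants would have to create an account and sync a study device before consenting.
2. Move the shared set-up (charging instruction, account creation, sub-steps 1 to 18, first sync) out of Sections 2.7 and 2.8 into a new step after Section 2.5 and before the Section 2.6 folder draw.
3. Add a post-consent field, 'set-up and first sync completed', that must be yes before a folder is drawn.
4. Count failures in the CONSORT flow as consented but not randomised.
5. Leave only the Boomerang or MapTrek link and the instruction packet after allocation.
6. The SAP is written in the past tense, so reordering cannot help participants already enrolled. For them, report by arm how many randomised participants had no step data.

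Cost: text is reordered and one field added, with the same staff doing the same steps at the same visit. Some set-up time goes to people who are then not randomised, and the results apply to veterans whose phone works with the device.

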### Section 2.4 Approaching the Patient

If you believe a patient is eligible for the study based on their CPRS data and discussions with the medical staff, approach the patient to see if they are interested in learning more and to finish any screening questions. You should only approach patients upon approval from the medical staff so that you don't disrupt clinic flow. Here is an example script (feel free to say in your own words as long as the major points are covered):

*"We are conducting a study with eligible participants to see if our map-based race will encourage Veterans to take more steps per day. We will randomize the participants to 2 different groups, a control group and an intervention group. The control group will receive a Fitbit, which is a small device that is worn on your wrist that measures your movements, to wear for approximately 9 weeks. At the end of the 9 weeks, they will complete an exit survey via phone call or online.*

*The intervention group will also be given a Fitbit and asked to wear it for approximately 9 weeks, but they will also be enrolled in a map-based race. You will be notified about your progress in the race via text message and you may also receive challenges where you can earn extra steps in the race. At the end of the 9 weeks, they will also complete an exit survey that asks about their experiences with the study.*

*Is this something that you'd like to learn more about or might be interested in participating in?"*

If the person indicates that they'd like to learn more about the study or want to participate, be sure to complete any remaining fields on the Screening Survey (Appendix A).

If any of these criteria are not met, the person is ineligible for the study. Please explain the reason for their ineligibility and thank them for their time.

If all criteria are met, you should continue on with the informed consent procedures in a room that is approved by the medical staff to avoid disrupting the clinic flow.

